22.3. Rating

The Investigator will assess the severity and relationship of all adverse effects. The following definitions will be used for severity assessment:

For all ADE and UADE reported, the Investigator will assign independent ratings for Severity and Relatedness to laser treatment in accordance with the descriptions found in Table 4 and Table 5, respectively.

Table 4: Severity Rating System for ADE/UADE

Score	Severity	Definition
0	None	Normal
1	Trace	Very minimal reaction resolved within 24 hours. Does not require medical intervention. No effect on daily activities.
2	Mild	Noticeable reaction expected to resolve within 7 days. Does not require medical intervention. No effect on daily activities.
3	Moderate	Noticeable reaction lasting more than 2 weeks. Possibly requires some medical intervention. May interfere with some daily activities.
4	Severe	Significant skin reaction lasting more than 6 months, or deemed permanent by Investigator. Requires significant medical or surgical intervention. Debilitating and prevents normal everyday activities

Table 5: Relatedness Rating System for AE/UADE

Score	Relatedness to Treatment	Definition
0	Not Related	Clearly related to other factors and not to laser treatment
1	Possibly Related	A reasonable temporal sequence from the time of study treatment but could have been produced by other factors
2	Probably Related	A reasonable temporal sequence from the time of study treatment but cannot be reasonably explained by other factors.
3	Related	A reasonable temporal sequence from the time of or stopping the investigational product, or reappears on repeat exposure, or there is a positive reaction at the application site.
U	Unable to Determine	Insufficient information to make a rational determination.

23. Investigational Sites

Investigational sites will be identified by the Sponsor and pre-qualified for participation prior to site initiation or subject enrollment.

24. Compensation

Subjects will receive PicoWay™ laser treatments in this study at no cost. Subjects will also receive a one-time honorarium of \$100.00 upon completion of the scheduled 12-week follow-up visit. Subjects consenting to skin punch biopsies will receive \$250.00 for each biopsy taken.

25. Monitoring Plan

Study Monitoring will be performed by qualified personnel from or designated by the Sponsor to ensure data integrity, adherence to the protocol and protection of study subjects. It is anticipated that at least three study monitoring visits will be scheduled per site during this study, though the Sponsor may determine that additional monitoring visits are required.

26. Protocol Deviation Reporting

Subjects enrolled without meeting inclusion/exclusion criteria, enrolled without providing informed consent and any other major deviations from the protocol will be reported to the Sponsor as soon as possible after becoming aware of the deviation. Protocol deviations will be reported to the IRB in accordance with IRB guidelines.

27. Record Retention

The Investigator will retain a copy of all study records in accordance with applicable regulations for a period of two (2) years after the study is terminated or completed. It is the responsibility of the Investigator to retain study records in a secure location at the site.

28. Publication Policy

Study Investigators agree not to publish the results from, or disclose confidential information related to, this study as described in the Clinical Trial Agreement without prior written agreement from the study Sponsor, Candela Corporation. If the Sponsor agrees to publish the results from this study, the Investigators will provide the Sponsor publication manuscript(s) for review at least thirty (30) days before submission for publication. Investigators will also provide the Sponsor advance at least (30) days' notice of any planned presentation of study results.

29. References

- Appendix D: Subject Satisfaction Survey
- Appendix E: Local Skin Response

30.1. Appendix A: Pigment Clearance Score Pigment Score

Score	Clearance	Description
1	0% - 24%	Poor response
2	25 - 49%	Fair Response
3	50 - 74%	Good response
4	75 - 94%	Excellent response
5	$\geq 95\%$	Complete response

30.2. Appendix B: Fitzpatrick Wrinkle Score (FWS)

Class	Wrinkling	Score	Degree of Elastosis
I	Fine wrinkles (rhytides)	1-3	Mild (fine textural changes with subtly accentuated skin lines)
II	Fine to moderate depth wrinkles,	4-6	Moderate (distinct papular elastosis [individual papules with yellow translucency under direct lighting] and
III	Numerous lines, with or without redundant skin folds Fine to deep wrinkles.	7-9	Severe (multipapular and confluent elastosis [thickened yellow and pallid] approaching or consistent with cutis rhomboidalis)

30.3. Appendix C: Subject Pain Scale

Question: How much pain did you experience during the treatment today?												
No Pain											Extreme Pain	
0	1	2	3	4	5	6	7	8	9	10		

30.4. Appendix D: Subject Satisfaction Scale

Question: How satisfied are you with your pigment improvement at this point of the study?	
Score	Definition
-2	Extremely Dissatisfied
-1	Somewhat Dissatisfied
0	Neither Satisfied nor Dissatisfied
1	Somewhat Satisfied
2	Extremely Satisfied

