After successful completion of the 12 week follow-up visit, subjects will be exited from the study.

7. Study Population

Up to 160 subjects will be enrolled in this study at up to two (2) investigational sites in the United States.

The Study Population will be enrolled at the discretion of the Investigator after determining that eligible subjects have unwanted benign pigmented lesions including dyschromia on the face, scalp, neck, chest, back, arms, hands, legs or feet; or wrinkles including fine lines on the face.

[figure not shown]
Subjects will be assessed at the Screening Visit and allocated to one **or both** study sub-groups if eligible:

Group A: Benign Pigmented Lesions including dyschromia

Group B: Wrinkles including fine lines

The logic scheme used for group allocation is provided below in Figure 1.

Figure 1: Study Group Allocation Logic

All subjects must satisfy the inclusion and exclusion criteria and provide signed informed consent to be eligible for participation in the study. Subjects enrolled in the study can discontinue their participation at any time for any reason without prejudice or reduction in the quality of their medical care. The Investigator or Sponsor can terminate a subject's participation in this study at any time to protect the subject's health or if a subject fails to

follow directions that result in noncompliance with study procedures. Subjects who withdraw or are terminated from the study prior to completion may be replaced.

8. Inclusion / Exclusion Criteria

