9.4. Subject Satisfaction Survey

At each study visit beyond Treatment Visit #1 the subjects will be asked to rate their level of satisfaction with the treatment results so far using a 5-point Subject Satisfaction Survey ranging from -2=Extremely Dissatisfied to 2=Extremely Satisfied. The Satisfaction Survey is provided in Appendix D.

10. Study Visit Procedures

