10.3. Follow-Up Visits

Subjects will be scheduled for follow-up visits at 4 ± 1 weeks, 8 ± 2 weeks, and 12 ± 2 weeks after their final study treatment visit, or approximately 1, 2 and 3 months. Additional visits may be scheduled by the Investigator as needed.

Photography

Treatment areas will be photographed at all follow-up visits using the same camera settings used previously at Baseline and Treatment Visits.

Subject Satisfaction

Subjects will be asked to rate their level of satisfaction with the study treatments thus far at each follow-up visit using the Subject Satisfaction Scale provided in Appendix C.

Skin Biopsy (optional)

Subjects who have provided prior written consent may have one or more skin biopsy taken from the treated area at the discretion of the Investigator. Biopsy procedure details are provided in the Treatment Visit section above.

11. Schedule of Events

The Study Schedule of Events is provided in Table 1.

NOTE: The Screening and Baseline / Treatment #1 Visits may be combined in the same visit.

NOTE: Fewer than four (4) Treatment Visits may be required to reach maximum expected clinical results in some subjects. Treatments may therefore be stopped, and subject placed into the Follow-Up phase at the discretion of the Investigator.

Table 1: Study Visits and Schedule of Events

Activity	Screening	Baseline Tx 1	Tx 2	Tx 3	Tx 4	1 Month Follow- Up	2 Month Follow- Up	3 Month Follow- Up
	0 to -2 Weeks	Day 0	Week 6 ± 2 Weeks	Week 12 ± 2 Weeks	Week 18 ± 2 Weeks	Week 22 ± 2 Weeks	Week 26 ± 2 Weeks	Week 30 ± 4 Weeks
Informed Consent	X							
Medical History/Concomitant Medications	X							
Inclusion/Exclusion Criteria	X							
Treatment Site ID	X							
Pregnancy Test	X	X	X	X	X			
Skin Biopsy (Optional)		X	X	X	X	X	X	X
Telephone Contact*		X	X	X	X			
Photography		X	X	X	X	X	X	X
Laser Treatment		X	X	X	X			
Subject Pain Score		X	X	X	X			
Subject Satisfaction			X	X	X	X	X	X
Safety Assessment (LSR, ADE, UADE)		X	X	X	X	X	X	X
Concomitant Medications	X	X	X	X	X	X	X	X
Study Exit								X

*10 Days post-treatment (+/- 7 Days)

12. Study Compliance

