17.3. Secondary Endpoints

1. Benign Pigmented Lesions

Percentage of subjects demonstrating Pigment Clearance Score (PCS) of 3 or 4 (> 50% improvement) comparing baseline to 12-week follow-up as determined by blinded physician evaluators from clinical photographs

2. Wrinkles

Percentage of subjects demonstrating ≥ 1 score improvement in Fitzpatrick Wrinkle Score (FWS) from baseline to 12-week follow-up visit as determined by agreement of 2 out of 3 blinded physician evaluators from clinical photographs

3. Subject Satisfaction

Mean and distribution of Subject Satisfaction Scores at all visits beyond Treatment Visit #1

4. Subject Pain

Mean and distribution of Subject Pain Scores following each treatment

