19.1. Statistical Plan Overview

The study will be conducted with two separate strata (pigment, wrinkles) which will be evaluated. Benign pigmented lesions including dyschromia (Group A) and wrinkles including fine lines (Group B) will be separately powered and analyzed for efficacy and safety while both groups will further be combined for safety analyses. All study sites will be eligible to enroll subjects into each stratum; no subject will be enrolled into both strata.

Subjects participating in the pigment treatment stratum will be evaluated using the Pigment Clearance Score (Appendix A) while subjects participating in the wrinkle treatment stratum will be evaluated using the Fitzpatrick Wrinkle Score (Appendix B). All study subjects will also be evaluated using the Subject Pain Scale (Appendix C), Subject Satisfaction Survey (Appendix D), the Local Skin Response (Appendix E), and will be evaluated for safety according to 21 CFR Part 812 as well as ICH guidelines (E3 and E6) and ISO 14385:2016 as applicable.

A statistical analysis plan (SAP) will be finalized prior to study initiation. The database will be constructed using Microsoft Office Excel (Microsoft, Redmond, WA). The database will be locked following a review of all protocol deviations to be classified as a major or minor deviation. Major and minor protocol deviations will be reviewed once all data undergo source document verification and prior to database lock. The independent biostatistician will determine major vs. minor protocol deviations.

Data analyses will be performed using SAS Version 9.3 or later (SAS Institute, Cary NC) and StatXact Version 10 or later (StatXact, Cambridge MA). All analyses will be performed in a GCP environment controlled by SOPs.

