19.4. Effectiveness Analyses

The skin pigmentation score will be evaluated using a paired t-test separately for the peri-orbital, peri-oral, and combined outcomes from baseline to study exit. In addition, the percentage achieving a 1-point improvement will also be displayed with two-sided 95% confidence intervals to support regulatory submissions requiring 1-point improvement analyses.

Wrinkle score improvement will be evaluated using a two-sided exact binomial test.

The Subject Pain Scale and Subject Satisfaction Score will be evaluated by displaying the distributions with the range, mean, and two-sided 95% confidence intervals provided. Results will be displayed separately for Groups A and Group B.

The effectiveness analyses will be performed using a Per Protocol (PP) population which excludes subjects with major protocol deviations such as subjects withdrawn prior to final evaluation.

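### The only satisfaction form asks about pigment, so for wrinkle-only subjects it does not measure satisfaction with the condition treated

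*Combined protocol and SAP*

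**What the plan says.** Section 9.4 describes the instrument in general terms: at each visit after the first treatment, subjects "rate their level of satisfaction with the treatment results so far" on a five-point scale. Sections 10.2 and 10.3 speak of satisfaction with the study treatments to date. None of the three is limited to one indication.

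Section 19.1 assigns the form to everyone: "All study subjects will also be evaluated using the Subject Pain Scale (Appendix C), Subject Satisfaction Survey (Appendix D", followed by the local skin response form.

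The form in Appendix D holds one question: "How satisfied are you with your pigment improvement at this point of the study". The answers run from -2 to 2.

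Section 17.3 lists the endpoint as "Mean and distribution of Subject Satisfaction Scores at all visits beyond Treatment Visit #1", without restricting it to the pigment group. Section 19.4 plans distributions, range, mean and two-sided 95% confidence intervals for the pain and satisfaction scores, and adds "Results will be displayed separately for Groups A and Group B". The second group is "Group B: Wrinkles including fine lines".

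For follow-up visits, Section 10.3 has satisfaction rated "using the Subject Satisfaction Scale provided in Appendix C". Appendix C is the pain scale.

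**The concern.** A subject treated only for wrinkles is asked to rate improvement in pigment, which was not the target of treatment. The plan nevertheless promises a Group B satisfaction mean, distribution and confidence interval. If the form is used as printed, those figures would carry the label of satisfaction with treatment while resting on a question about something else. Because the defect lies in the question put to the subject, it has to be corrected before data are collected; reanalysis cannot supply the missing answer.

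**Working it through.** This is mainly a comparison of texts. The plan states no figure to reproduce, and the point depends on no error rate, power, effect size or standard deviation.

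**Step 1: the construct intended.** Section 9.4 refers to treatment results; Sections 10.2 and 10.3 refer to the study treatments. Either suits both indications.

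**Step 2: the construct on the form.** Appendix D names pigment improvement only. It has no wrinkle wording, no neutral wording and no space to enter the indication. Form and procedure text therefore disagree.

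**Step 3: who receives the form.** Under Section 19.1, all subjects in both strata. The synopsis list of instruments also names Appendix D as the satisfaction scale and offers no alternative.

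**Step 4: whether a Group B result depends on it.** It does. Section 17.3 sets no restriction by group, and Section 19.4 reports by group.

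**Step 5: what does not depend on it.** The primary endpoints (Section 17.1) come from blinded scoring of photographs. The hypotheses and sample sizes (Sections 19.2 and 19.3) do not use satisfaction. For Group A, the question names the condition treated.

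**Step 6: how many scores are involved.** Inputs:
- up to four treatments, with earlier stopping allowed at the investigator's discretion (Section 6)
- a rating at each treatment visit after the first and at three scheduled follow-up visits (Section 11, Table 1)
- 34 evaluable wrinkle subjects (Section 19.3)

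With T treatments and all three follow-up visits attended, scores per subject = (T - 1) + 3.
- T = 1: 0 + 3 = 3 scores; 34 x 3 = 102
- T = 4: 3 + 3 = 6 scores; 34 x 6 = 204

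The range for 34 subjects is 102 to 204. The 34 is the number needed for power, not an enrolment figure. The protocol allows up to 160 subjects in total and gives no split by group, so the actual count could be larger.

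**Step 7: subjects in both groups.** The synopsis and Section 7 allow allocation to both groups; Section 19.1 says no subject will be enrolled into both strata. If Section 19.1 governs, every Group B subject is wrinkle-only. If Section 7 governs, a subject in both groups has a usable pigment rating and no wrinkle rating.

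**The case against.** The best defence is that the procedure text is right. Sites are told in Section 9.4 to ask about treatment results and in Sections 10.2 and 10.3 to ask about the study treatments; the case report forms are not in the documents, so the wording used in practice may differ from Appendix D. That stands as a limit on what can be known. It does not remove the conflict, because the plan names Appendix D as the form for all subjects and provides no other.

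It is also fair to say that the endpoint is descriptive. It has no hypothesis, power calculation or success criterion. That stands and sets the ceiling on how much this matters.

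Four stronger readings are tempting, and the documents do not support them:

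- **Wrinkle subjects' answers will drift towards neutral.** Nothing in the documents shows how they would answer. The point does not need a direction: a rating of pigment improvement is not a rating of wrinkle results, whichever way it falls.
- **204 scores will be lost.** That pairs a power-based number of evaluable subjects with the maximum number of scheduled assessments. It is neither an expected count nor an upper bound.
- **Subjects in both groups will never be asked about wrinkles.** This assumes that such subjects exist, and the protocol contradicts itself on that.
- **Follow-up satisfaction will be collected on the pain scale.** The reference to Appendix C in Section 10.3 is a clerical slip. The synopsis and Sections 9.4, 10.2 and 19.1 all give Appendix D, and Appendix C is plainly a pain question. The slip adds nothing to the measurement argument.

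**Conclusion.** The point holds as an internal inconsistency between the satisfaction form and the procedure text. For wrinkle-only subjects, Appendix D as printed does not measure satisfaction with the condition treated, so the separate Group B result cannot be read as satisfaction with wrinkle results. Every wrinkle-only subject is affected at every assessment.

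The count of 102 to 204 scores assumes 34 Group B subjects, full attendance at the three scheduled follow-up visits, and no extra visits. The conclusion itself rests on one assumption: that the form is used as the plan directs. It does not extend to the primary endpoints, the sample sizes or Group A satisfaction. The change should be made because it is cheap and the loss could not be recovered later, but it does not threaten the trial's main conclusions.

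**What to change.** Before first use:

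1. Reword the Appendix D question to match Section 9.4, for example by asking about satisfaction with the treatment results, or with the improvement in the treated condition. One neutral wording is enough if each subject belongs to one group only.
2. Reconcile the synopsis and Section 7 with Section 19.1 on whether a subject may be in both groups. If dual allocation is kept, collect one rating per indication, because a single neutral question would not separate the two.
3. As a clerical correction, change the satisfaction scale reference in Section 10.3 from Appendix C to Appendix D.

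The cost is one line on a form and one cross-reference. A second rating is needed only for subjects in both groups, if there are any. Sample size and the planned summaries in Section 19.4 stay as they are. If the case report forms already carry a suitable Group B wording, Appendix D should be brought into line with them.

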30.5. Appendix E: Local Skin Response

Local Skin Response Assessment				
 None  N/A				
 Erythema	 Edema	 Whitening	 Petechiae	 Pinpoint Bleeding
 None  Trace  Mild  Moderate  Severe	 None  Trace  Mild  Moderate  Severe	 None  Trace  Mild  Moderate  Severe	 None  Trace  Mild  Moderate  Severe	 None  Trace  Mild  Moderate  Severe
 Purpura	 Crusting	 Blister	 Burn	 Other:
 None  Trace  Mild  Moderate  Severe	 None  Trace  Mild  Moderate  Severe	 None  Trace  Mild  Moderate  Severe	 None  Trace  Mild  Moderate  Severe	 None  Trace  Mild  Moderate  Severe
 Other:	 Other:	 Other: _____	 Other: _____	 Other:
 None  Trace  Mild  Moderate  Severe	 None  Trace  Mild  Moderate  Severe	 None  Trace  Mild  Moderate  Severe	 None  Trace  Mild  Moderate  Severe	 None  Trace  Mild  Moderate  Severe
